9.7.3.2. Administration using the Mk II Inserter

The intravitreal injection procedure should be carried out under aseptic conditions, which include use of sterile gloves, a sterile drape, a sterile caliper, and a sterile eyelid speculum (or equivalent). Adequate anesthesia and a broad-spectrum microbicide should be given prior to the injection.

- 1. Optimal placement of the FAI insert is inferior to the optic disc and posterior to the equator of the eye. Measure 4 millimeters inferotemporal from the limbus with the aid of calipers for point of entry into the sclera.
- 2. Using sterile procedure, open the sterile foil pouch containing the Mk II inserter in its tray.
- 3. Remove the sterile tray lid and then remove the Mk II inserter from the sterile tray.
- 4. Carefully remove the protective cap from the needle and inspect the needle tip to ensure it is not bent.
- 5. Visually check through the viewing window of the inserter to confirm that the ambercolored FAI insert is present.
- 6. Gently displace the conjunctiva so that after withdrawing the needle, the conjunctival and scleral needle entry sites will not align. Care should be taken to avoid contact between the needle and the lid margin or lashes.
- 7. Insert the needle through the conjunctiva and sclera up to the hub of the inserter.
 - a. If the Investigator is unable to insert the needle through the conjunctiva and sclera, please contact the monitor and sponsor immediately.
- 8. Press the button on the top of the inserter and confirm that the spring-loaded slide retracts with an audible "click".
- 9. Depress the plunger at the back of the inserter fully to deliver the FAI insert into the back of the eye.
- 10. Remove the Mk II inserter from the eye and discard.
- 11. Remove the lid speculum and perform indirect ophthalmoscopy to verify adequate central retinal artery perfusion, absence of any other complications, and to verify the placement of the insert.
 - a. If the FAI insert is observed to be misplaced within the eye, please contact the monitor and sponsor immediately. Administration of a second FAI insert within the study eye is not permitted in this protocol.

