10. INVESTIGATIONAL MATERIALS

10.1. FAI Insert

The FAI insert is an injectable intravitreal sustained-release FA delivery system pre-loaded into an injection device. Each insert contains a drug core of FA as the active ingredient within a cylindrical polyimide polymer tube 3.5 mm long with an external diameter of 0.37 mm. One end of the tube is capped with an impermeable polymer (silicone adhesive); the other end is capped with a permeable polyvinyl alcohol membrane. FA release occurs through the permeable end of the cylinder. Each FAI insert contains 0.18 mg FA and delivers FA into the vitreous humor for 36 months, as demonstrated in a clinical pharmacokinetics study of Iluvien (Campochiaro 2013). In vitro data demonstrate that initial FA release occurs at a rate of approximately 0.2 μ g FA/day, gradually decreasing over three years to a rate of approximately 0.1 μ g FA/day. The FAI insert is designed to be injected through the pars plana into the vitreous.

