13. ASSESSMENT OF UTILIZATION AND SAFETY

13.1. Primary Utilization Endpoint

The primary utilization endpoint is defined as the proportion of intravitreal insertion procedures that are assessed by the Investigator as satisfactory. A satisfactory procedure is defined as one receiving a score from the Investigator as either Very Easy (VE), Easy (E), or Routine (R), according to the following categories:

- Very Easy (VE)
- Easy (E)
- Routine (R)
- Difficult (D)
- Very Difficult (VD)

Please refer to Section 20 for additional information.

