20. APPENDIX 3: QUESTIONNAIRES

20.1. Mk I Questionnaires

20.1.1. Investigator Questionnaire

- Were the instructions for the use of the Mk I inserter clear and understandable? If not, please explain.
- 2. The ease of intravitreal administration using the Mk I inserter was:
 - a. Very easy
 - b. Easy
 - c. Routine
 - d. Difficult
 - e. Very difficult
- Were you able to deliver the insert into the vitreous using the Mk I inserter? If not, please explain.

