20.2. Mk II Inserter Questionnaires

20.2.1. Investigator Questionnaire

- Were the instructions for the use of the Mk II inserter clear and understandable? If not, please explain.
- 2. The ease of intravitreal administration using the Mk II inserter was:
 - a. Very easy
 - b. Easy
 - c. Routine
 - d. Difficult
 - e. Very difficult
- Were you able to deliver the insert into the vitreous using the Mk II inserter? If not, please explain.

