8.1. Primary Utilization Endpoint

The primary utilization endpoint is defined as the proportion of intravitreal insertion procedures that are assessed by the Investigator as satisfactory. A satisfactory procedure is defined as one receiving a score from the Investigator as either Very Easy (VE), Easy (E), or Routine (R), according to the following categories:

- Very Easy (VE)
- Easy (E)
- Routine (R)
- Difficult (D)
- Very Difficult (VD)

If more than one inserter is used for the same eye, the results from the first inserter will be used for completing the questionnaires and analysis. Comments related to the second inserter will be presented in a listing. Any injector which penetrates the eye but does not deliver the FAI insert into the eye will be scored as Very Difficult for analysis.

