8.2. Secondary Utilization Endpoints and Analysis

Secondary endpoints include:

- Clarity of the instructions for use, as assessed by the Investigator (yes, no)
- Differences between observed procedure and instructions for use, as assessed by an Observer (yes, no)

These secondary utilization endpoints will be analyzed employing descriptive statistics. Additionally descriptive statistics for other items on the investigator and observer questionnaires will be presented.

9. Safety Analysis

Safety analyses will be performed by treatment group for the Safety population at Day 7 and Month 12. Descriptive statistics will be used in safety analyses. Summary at the subject level will also be provided.

Non-treated randomized eyes and non-study eyes will only have all safety data listed. Adverse events will be summarized for these eyes, but otherwise they will not be included in safety tabulations.

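### The SAP rescores a failed delivery only if the insert does not get into the eye, while the questionnaire asks about the vitreous, so an eye with delivery item 3 answered No can still count as satisfactory

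*SAP*

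**What the plan says.** Protocol 13.1 defines the primary endpoint by the rating alone: "The primary utilization endpoint is defined as the proportion of intravitreal insertion procedures that are assessed by the Investigator as satisfactory". SAP 8.1 repeats this and adds the cut: "A satisfactory procedure is defined as one receiving a score from the Investigator as either Very Easy (VE), Easy (E), or Routine (R"). Neither definition includes a condition on where the insert ends up.

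SAP 8.1 then adds the only override based on outcome: "Any injector which penetrates the eye but does not deliver the FAI insert into the eye will be scored as Very Difficult for analysis". Protocol 13.1 and 14.3.4.1 contain no override.

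Delivery is also asked about directly. Item 3 of the Investigator questionnaire reads "Were you able to deliver the insert into the vitreous using the Mk I inserter" for one device (Protocol 20.1.1) and "Were you able to deliver the insert into the vitreous using the Mk II inserter" for the other (Protocol 20.2.1). SAP Appendix 13.2 carries the same items. The vitreous is the design target according to Protocol 10.1: "The FAI insert is designed to be injected through the pars plana into the vitreous".

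Item 3 has no role in the primary endpoint. SAP 8.2 covers it only in a general commitment: "Additionally descriptive statistics for other items on the investigator and observer questionnaires will be presented".

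Under SAP 8.1.1 and Protocol 14.3.4.1, the trial succeeds if the Mk II satisfactory proportion is not numerically below the Mk I proportion.

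**The concern.** The SAP has already accepted that an ease rating is not enough when the device fails to deliver. What remains is where the line falls, and the documents use two different standards. The override tests for the eye. The questionnaire tests for the vitreous, which is the design target and the site named in the endpoint's own word, intravitreal.

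An insert in the eye but outside the vitreous falls between the two. Item 3 would be No, the override would not apply on its literal wording, and a rating of Routine or better would stand. A procedure that the trial's own questionnaire records as a failed delivery would then count toward success, in whichever arm it occurred. Because the success rule has no margin, one such eye can decide the declared result.

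**Working it through.** **1. Inputs.** Planned eyes: 20 Mk II and 10 Mk I (SAP 4.1). Success rule: SAP 8.1.1. Override: SAP 8.1. Item 3: Protocol 20.1.1 and 20.2.1.

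**2. The plan's own figures.** The exact binomial 95% interval has lower limit Beta(0.025; x, n − x + 1) and upper limit Beta(0.975; x + 1, n − x).
- 10/20 gives 27.2% to 72.8%.
- 5/10 gives 18.7% to 81.3%.

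Both match SAP 4.1, and each is the widest interval for its sample size, as stated there.

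**3. The rules side by side, for an eye that was penetrated.**

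| Where the insert ends up | Item 3 | SAP 8.1 override, read literally | Score used |
|---|---|---|---|
| Not in the eye | No | Applies | Very Difficult |
| In the eye, outside the vitreous | No | Does not apply | Investigator's rating |
| In the vitreous, not optimally positioned | Yes | Does not apply | Investigator's rating |
| In the vitreous, well positioned | Yes | Does not apply | Investigator's rating |

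Only the second row is in dispute. There the override and item 3 disagree on whether delivery failed.

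**4. What one eye is worth.** Let x2 be the satisfactory count for Mk II and x1 that for Mk I. Success requires x2/20 ≥ x1/10, that is x2 ≥ 2·x1. One Mk II eye is 1/20 = 5 points; one Mk I eye is 1/10 = 10 points.

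- *One Mk II eye rescored.* Success turns to failure exactly when x2 = 2·x1, for every x1 from 1 to 10. Examples: 20/20 v 10/10 becomes 19/20 (95%) v 10/10 (100%); 18/20 v 9/10 becomes 17/20 (85%) v 9/10 (90%).
- *One Mk I eye rescored.* Failure turns to success when Mk II is one or two eyes short. Example: 18/20 or 19/20 v 10/10 fails, but against 9/10 either succeeds, since 2 × 9 = 18.

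**5. How often a tie would arise.** The documents give no expected satisfactory rate, so this is an assumption: the same true rate p in both arms and independent eyes. The tie probability is the sum over x1 of Bin(2·x1; 20, p) × Bin(x1; 10, p).

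| Assumed p | Probability of a tie |
|---|---|
| 80% | 0.13 |
| 90% | 0.17 |
| 95% | 0.28 |
| 99% | 0.74 |

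The tie, where one Mk II eye decides, is therefore not a remote case if ratings are high. These figures describe how fragile the rule is. They do not say how often an insert would lie outside the vitreous, which cannot be computed from the documents.

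**The case against.** Several parts of the opposing case stand and limit the point.

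- *The phrase may have been meant as the vitreous.* In Protocol 9.7.3.1 and 9.7.3.2, step 9 describes intended delivery as into the back of the eye, and the SAP sentence sits in a section on intravitreal procedures. A deliberately looser standard is one reading only. If the vitreous was meant, the correction changes nothing but the wording.
- *The protocol's misplacement step does not prove the gap.* A reader might infer that the protocol foresees inserts outside the vitreous from step 11a: "If the FAI insert is observed to be misplaced within the eye, please contact the monitor and sponsor immediately". But step 1 of the same lists describes an optimal location, and an insert can be in the vitreous yet away from it. Only item 3 tests the vitreous.
- *The rating may already reflect the failure.* It is tempting to argue that misplacement is found after the handling has been rated. The documents do not say that the rating comes before ophthalmoscopy. The questionnaire follows the administration, and ophthalmoscopy is step 11 of that procedure. An Investigator who answers No to item 3 may well choose Difficult.
- *A difference between arms is conjecture.* The needles differ in gauge and retraction (Protocol 5.5 and 5.6), but the documents give no misplacement data for either device.
- *The event is not hidden.* SAP 8.2 summarises item 3 and SAP 8 lists utilization data, so a reader could recount.
- *The leverage comes from the success rule.* Any one-eye change reverses a tie, and SAP 8.1.1 calls the formal between-arm comparison exploratory.
- *The endpoint is ease, not placement accuracy.* That is true of the protocol definition. The SAP has nevertheless already added a delivery condition, so aligning it with item 3 adds no new principle.

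What survives is the literal mismatch in the second row of the table, in a rule that feeds the primary endpoint.

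**Conclusion.** The point holds as a wording gap with a contingent effect. Read literally, SAP 8.1 allows an eye with item 3 answered No to count as satisfactory, and nothing else in either document links item 3 to the primary endpoint.

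The effect is zero if no insert lies in the eye outside the vitreous, or if every such procedure is rated Difficult or Very Difficult. If one Mk II eye is affected and the counts are tied, the declared result reverses; one Mk I eye can reverse it in the other direction. This assumes 20 and 10 analysed eyes and the success rule as written.

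The documents do not support the stronger conclusions that such eyes are expected, that they would favour Mk II, or that every insert described as misplaced should count as unsatisfactory. This is a cheap improvement to make before results are seen. It does not show that the endpoint is invalid.

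**What to change.** In SAP 8.1, replace the override sentence with: *Any first inserter that penetrates the eye and for which Investigator item 3 (delivery into the vitreous) is answered No will be scored Very Difficult for analysis.* Apply it to both arms. An insert that does not enter the eye at all also gives No on item 3, so the new sentence still covers the present case.

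Two limits should be kept:
- Do not rescore an insert that is in the vitreous but not optimally positioned.
- Do not use the Day 1 placement check as a second trigger unless a recorded insert-location field is confirmed. The schedule of assessments requires placement to be verified, but SAP 9.2.3 describes only tissue status, perfusion and complications. It names no location field.

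If the sponsor prefers to leave the primary scoring alone, the fallback is a pre-specified sensitivity analysis that counts item 3 = No as unsatisfactory in both arms.

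The cost is one SAP sentence and no new data, since item 3 is already asked after each administration. The downside is that the satisfactory proportion may be slightly lower in either arm.

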8.1.1. Primary Utilization Analysis

The primary utilization analysis will compare the proportion of intravitreal insertion procedures that are assessed by the Investigator as satisfactory (i.e., VE, E or R), in the Mk I inserter and the Mk II inserter groups.

The number and percentage of eyes with satisfactory intravitreal insertion procedures will be presented, for the Mk I inserter and the Mk II inserter groups of eyes employing descriptive statistics including 95% confidence intervals using the exact binomial methodology. The difference in proportions, the 95% exact unconditional confidence interval for the treatment difference (Mk II vs Mk I) in proportions, and the Fisher's exact test p-value will also be provided, however this comparison is considered exploratory only as the study is not powered to detect a difference between the inserters.

The primary utilization analysis will be conducted after all eyes in the study have completed study Day 7 or have discontinued study participation.

The study will be deemed a success for the Mk II inserter if the following condition is met: The proportion of Mk II procedures scored as satisfactory is not numerically lower than the corresponding proportion of Mk I procedures.

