7.2. Number of Subjects

A total enrollment of approximately 30 eyes is planned for this study. Enrollment of approximately 25 subjects is expected, and will continue until:

- at least 20 and 10 study eyes each have been treated using the Mk II and Mk I inserters, respectively, and
- at least 10 different investigators each have performed at least one administration procedure.

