7.5. Measures Taken to Minimize Bias

At least 10 different investigators will administer the FAI insert, and randomization will be stratified by investigator.

Each time a subject's eye is enrolled in the study, one investigator will serve as the treating investigator (Investigator); another person will serve as the trained observer (Observer). On study Day 1, the Investigator will administer the FAI insert, and the Observer will observe the procedure used by the Investigator to administer the FAI insert. The Investigator and the Observer will complete questionnaires related to the administration of the FAI insert on Day 1. The Investigator (or designee) will perform all subsequent study assessments. Study personnel will not disclose to the subject which inserter was used for intravitreal administration of the FAI insert.

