3.1. Overall Study Design and Plan

This trial is a 12 month, phase 3, multi-center, randomized, single-masked (subject), controlled study designed to evaluate the utilization and safety of the Mk II inserter and the safety of the FAI insert, in subjects with non-infectious uveitis affecting the posterior segment of the eye. This study will be conducted in at least 3 study sites. Enrollment of approximately 25 subjects is expected. A total enrollment of approximately 30 eyes is planned for this study (20 Mk II inserter: 10 Mk I inserter) in one or both eyes in each subject.

All subjects will receive the FAI insert on Day 1 of the study, administered using either an Mk I inserter or an Mk II inserter. If both eyes in a subject with bilateral uveitis satisfy the study's inclusion/exclusion criteria, both eyes may be enrolled in the study. In this case, randomization of a subject's second eye will occur independently and will occur no earlier than the study Day 7 visit for the subject's first study eye.

At least 10 different investigators will administer the FAI insert. Each time a subject's eye is enrolled in the study, one investigator will serve as the treating investigator (Investigator); another staff member in the study site will serve as the trained observer (Observer). On study Day 1, the Investigator will administer the FAI insert, and the Observer will observe the procedure used by the Investigator to administer the FAI insert. The Investigator and the Observer will complete questionnaires related to the administration of the FAI insert on Day 1. The Investigator (or designee) will perform all subsequent study assessments. Study personnel will not disclose to the subject which inserter was used for intravitreal administration of the FAI insert.

Subjects will receive standard care in the study eye(s) and any non-study eye for 12 months following enrollment, in accord with medical need and the Investigator's standard practice. Eyes will be assessed according to the schedule of procedures and assessments (Appendix 13.1).

Analyses of study data will be performed at the following two time points during the study:

- 1. After all subjects have completed the Day 7 visit (or have been discontinued from the study prior to this visit). The primary utilization and safety analyses of the inserters will be conducted at Day 7 time point.

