4.2. Designation of Study Eye(s) and Randomization

For subjects with unilateral uveitis, the study eye will be the affected eye. For subjects with bilateral uveitis, the study eye(s) will be the eye(s) meeting eligibility criteria. If both eyes satisfy eligibility criteria, both eyes may be enrolled in the study. In a subject with both eyes eligible for enrollment, randomization of the subject's second study eye may occur no sooner than study Day 7 of that subject's first study eye.

Following confirmation of eligibility at Day 1, eyes will be randomly assigned (2:1) to receive the FAI insert using either the Mk II inserter or the Mk I inserter, respectively. Randomization assignments will be administered through a central Interactive Web Response System (IWRS). Randomization will be stratified on the basis of the investigator administering the treatment. The randomization schedule will be prepared using a blocked randomization and will be generated by an independent statistician. Only those subjects who have been enrolled in the study will have data recorded on the electronic case report forms (eCRF).

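### The only Mk II versus Mk I comparison in SAP 8.1.1 leaves out the investigator strata used in the randomisation, which can make it conservative if investigators rate differently

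*SAP*

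**What the plan says.** **Randomisation.** SAP 4.2 states that "eyes will be randomly assigned (2:1) to receive the FAI insert using either the Mk II inserter or the Mk I inserter, respectively", using a blocked schedule, and that "Randomization will be stratified on the basis of the investigator administering the treatment". Protocol 7.5 lists this among the measures against bias: "At least 10 different investigators will administer the FAI insert, and randomization will be stratified by investigator". Protocol 7.2 asks only that "at least 10 different investigators each have performed at least one administration procedure", so a stratum may hold a single eye. About 30 eyes are planned, 20 Mk II and 10 Mk I.

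**Endpoint.** Under SAP 8.1 a procedure is satisfactory if the treating investigator rates it Very Easy, Easy or Routine. The stratification factor is therefore also the rater.

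**Analysis.** SAP 8.1.1 gives an exact binomial interval for each inserter, then the difference in proportions with "the 95% exact unconditional confidence interval for the treatment difference (Mk II vs Mk I) in proportions, and the Fisher's exact test p-value". No strata are named. The SAP adds that "this comparison is considered exploratory only as the study is not powered to detect a difference between the inserters". Success is a separate rule: "The proportion of Mk II procedures scored as satisfactory is not numerically lower than the corresponding proportion of Mk I procedures".

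**The concern.** Blocking within investigator keeps much of any difference in rating habits out of the Mk II minus Mk I contrast. An analysis that treats the eyes as two unstratified samples counts that variation as error again. The error is then overstated to the extent that investigators differ.

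What is at stake is limited but real. The success rule is a bare comparison of two proportions, so this interval and p-value are the only statement a reader gets of the uncertainty in the difference. The SAP gives no reason for setting the strata aside.

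**Working it through.** **1. The plan's own figures.** The Clopper-Pearson limits are the 0.025 quantile of Beta(x, n−x+1) and the 0.975 quantile of Beta(x+1, n−x). For 10/20 they are 27.2% and 72.8%; for 5/10 they are 18.7% and 81.3%. Both match SAP 4.1, and both are the widest possible at their n. These per-inserter intervals are not in question.

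**2. Inputs.** From the documents: 20 and 10 eyes, 2:1 blocked allocation, at least 10 investigators, at least one eye each. Assumed, because the documents are silent: blocks of 3, ICC between eyes of one investigator from 0 to 0.4, satisfactory rates, and loads per investigator. Two eyes of one subject are treated as independent.

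**3. Why ignoring strata can be conservative.** Take ten investigators with one full block each (two Mk II, one Mk I) and no true difference. Let σ² be the variance of one eye's result and ρ the ICC.

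- One investigator's contrast has variance σ²[(1+ρ)/2 + 1 − 2ρ] = 1.5σ²(1−ρ).
- The average over ten has variance 0.15σ²(1−ρ).
- The unstratified formula gives σ²(1/20 + 1/10) = 0.15σ².
- Unstratified SE over true SD is therefore 1/√(1−ρ): 1.00, 1.05, 1.12 and 1.29 at ρ = 0, 0.1, 0.2 and 0.4.

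Estimated SEs run slightly low at this sample size. In simulation the ratio was about 0.94 to 1.06 at ICC 0 to 0.1, and 1.23 at ICC 0.4 with three eyes each and 85% satisfactory. With uneven loads at ICC 0.1 to 0.2 it was 0.97 to 1.03, because incomplete blocks cancel less. These are SE ratios. They stand in for the exact unconditional interval, whose width was not simulated.

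**4. Power of Fisher's test against re-randomisation.** The re-randomisation statistic is T = crude Mk II proportion minus crude Mk I proportion. The p-value is the share of re-draws, made within investigator under the block scheme, with |T*| at least |T|. Investigator rates are beta-distributed, with Mk I averaging 50% and Mk II 40 points higher, capped at 100%. As an anchor, exact enumeration of Fisher's power for 90% v 50% at 20 v 10 eyes is 62.8%, which agrees with the ICC 0 column. The table gives two separate simulation runs, in percent.

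| Loads | Test | ICC 0 | 0.1 | 0.2 | 0.4 |
|---|---|---|---|---|---|
| 10 × 3, run A | Fisher | 63 | 54 | 46 | 32 |
| | Re-randomisation | 60 | 54 | 49 | 42 |
| | Difference | −3 | 0 | +3 | +10 |
| 10 × 3, run B | Fisher | 63 | 55 | 48 | 33 |
| | Re-randomisation | 60 | 56 | 51 | 40 |
| | Difference | −3 | +1 | +3 | +7 |
| Uneven, run A | Fisher | 63 | 55 | 47 | 34 |
| | Re-randomisation | 69 | 64 | 58 | 47 |
| | Difference | +6 | +9 | +11 | +13 |
| Uneven, run B | Fisher | 64 | 54 | 48 | 33 |
| | Re-randomisation | 69 | 63 | 58 | 46 |
| | Difference | +5 | +9 | +10 | +13 |

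Run B used 1,500 trials with 800 re-draws, and uneven loads of 6, 5, 4, 3, 3, 2, 2, 1, 1, 1, 1, 1. Simulation error on each of its power figures is up to √(0.5 × 0.5/1500) = 1.3 points. Compare tests within a column: the 100% cap lowers the Mk II average as ICC rises, so falls along a row are not all due to the strata.

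**5. Size.** In run B, with no true difference, re-randomisation rejected in 0.5% to 4.7% of trials and Fisher in 0.3% to 2.8%. Run A also stayed at or below 5%. A further run of 1,000 trials (uneven, ICC 0) gave 5.3% against 3.2% for Fisher; its simulation error is √(0.05 × 0.95/1000) = 0.7 points.

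**6. Stratified tests that would not help.** An exact conditional stratified test loses the investigators who used one inserter only. With a logit-normal investigator effect of SD 0, 1 and 2 and uneven loads, its power was 0.593, 0.527 and 0.388, against 0.710, 0.620 and 0.398 for Fisher. Re-randomising a within-investigator-centred statistic gave 56, 49, 46 and 34% on the twelve uneven loads, against Fisher's 64, 54, 48 and 33%. The choice of statistic matters.

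**The case against.** **Nothing is decided by this comparison.** The SAP calls it exploratory, SAP 4.1 says the study is not powered for a difference, and the success rule uses neither the interval nor the p-value. This stands and fixes the weight of the point.

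**The loss is not certain.** A reader might infer that the interval is simply too wide and that the test simply loses power. The documents do not support that. They give no ICC, block size, rates or loads. At ICC 0 with even loads Fisher is about 3 points better, and at ICC 0.1 the two are level. Nor do the documents say that the rater is expected to drive the score; Protocol 7.5 offers stratification only as a guard against bias.

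**Not all the gain comes from the strata.** With uneven loads re-randomisation gains 4 to 6 points even at ICC 0, where there is no investigator effect to recover. That part reflects Fisher's coarse reference distribution. This stands.

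**The power setting is favourable.** At 80% v 90% satisfactory, power was 1% to 8% for both tests with three eyes each, and 3% to 9% for Fisher against 8% to 13% with uneven loads. Neither test is informative there.

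**The success verdict is not shown to be wrong.** In simulations with no true difference and uneven loads, the crude and Mantel-Haenszel differences gave different success verdicts in 13% to 19% of trials. One might read this as a fault in the rule. It is not evidence of one: with no true difference the sign is largely chance, and the Mantel-Haenszel estimate drops one-inserter investigators.

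What remains is that the analysis departs from the randomisation scheme without a stated reason, and a test that follows the scheme is available at little cost.

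**Conclusion.** The mismatch is there in the text: randomisation is stratified by investigator, and the sole between-inserter interval and test are not. The consequence is conditional. If investigators differ in how they rate, the comparison can be conservative. Under the stated assumptions and ICC 0.1 to 0.4, Fisher gives up about 0 to 10 power points with ten investigators of three eyes and about 9 to 13 with uneven loads, of which about 5 are discreteness. With no investigator effect and even loads nothing is lost. The error does not inflate false positives and leaves the success rule untouched. This is a modest improvement to an exploratory result.

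**What to change.** In SAP 8.1.1:

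- **Add** beside the planned exploratory results a p-value from re-randomising inserters within investigator under the IWRS block scheme. Name the crude difference in proportions as the test statistic. Every eye is kept.
- **Keep** the exact unconditional interval and the per-inserter exact intervals. Note that the former may be conservative because it ignores the strata. A re-randomisation interval is not proposed: it would need an effect model for a binary outcome, and its coverage has not been checked.
- **Show** a Mantel-Haenszel difference stratified by investigator as a descriptive sensitivity result only, stating how many eyes drop out with one-inserter investigators.

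**Cost.** SAP wording and a short program that uses the existing block scheme; no new data. If investigators do not differ and loads are even, the added test has up to about 3 points less power than Fisher's, which is still reported.
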